#### 7.2 Evaluation of Safety

Analyses will be performed for all patients having received at least one dose of IMP. The study will use the CTCAE v5.0 for reporting of non-hematologic adverse events and modified criteria for hematologic adverse events.

### 7.3 Definitions of Adverse Events

#### 7.3.1 Adverse Event

An adverse event (also known as an adverse experience) is defined as any untoward medical occurrence associated with the use of a drug in humans, whether or not considered drug related. More specifically, an adverse event can be any unfavorable and unintended sign (e.g., an abnormal laboratory finding), symptom, or disease temporally associated with the use of a drug, without any judgment about causality. An adverse event can arise from any use of the drug (e.g., off-label use, use in combination with another drug) and from any route of administration, formulation, or dose, including an overdose.

Laboratory test value abnormalities will not be recorded as AEs unless they are designated as clinically significant, defined as any one of the following: symptomatic, requiring treatment, resulting in dose modification or delay or premature study withdrawal, or placing the subject at risk for other toxicity in the judgment of the treating investigator.

#### 7.3.2 Adverse reaction

An adverse reaction is defined as any adverse event caused by the use of a drug. Adverse reactions are a subset of all suspected adverse events for which there is reason to conclude that the drug caused the event.

#### 7.3.2.1 Suspected

A suspected adverse reaction is defined as any adverse event for which there is a reasonable possibility that the drug caused the adverse event. For the purposes of IND safety reporting, "reasonable possibility" indicates that there is evidence to suggest a causal relationship between the drug and the adverse event. A suspected adverse reaction implies a lesser degree of certainty about causality than an adverse reaction.

#### 7.3.2.2 Unexpected

An adverse event or suspected adverse reaction is considered unexpected if it is not listed in the investigator brochure or package insert(s), or is not listed at the specificity or severity that has been observed, or, if an investigator brochure is not required or available, is not consistent with the risk information described in the general investigational plan or elsewhere in the current application.

"Unexpected," as used in this definition, also refers to adverse events or suspected adverse reactions that are mentioned in the investigator brochure as occurring with a class of drugs or as anticipated from the pharmacological properties of the drug, but are not specifically mentioned as occurring with the particular drug under investigation.

Adverse events that would be anticipated to occur as part of the disease process are considered unexpected for the purposes of reporting because they would not be listed in the investigator brochure. For example, a certain number of non-acute deaths in a cancer trial would be anticipated as an outcome of the underlying disease, but such deaths would generally not be listed as a suspected adverse reaction in the investigator brochure.

Some adverse events are listed in the Investigator Brochure as occurring with the same class of drugs, or as anticipated from the pharmacological properties of the drug, even though they have not been observed with the drug under investigation. Such events would be considered unexpected until they have been observed with the drug under investigation. For example,

although angioedema is anticipated to occur in some patients exposed to drugs in the ACE inhibitor class and angioedema would be described in the investigator brochure as a class effect, the first case of angioedema observed with the drug under investigation should be considered unexpected for reporting purposes.

## 7.3.2.3 Serious

An adverse event or suspected adverse reaction is considered serious if, in the view of either the investigator or sponsor, it results in any of the following outcomes:

- Death
- Life-threatening adverse event
- Inpatient hospitalization or prolongation of existing hospitalization
- A persistent or significant incapacity or substantial disruption of the ability to conduct normal life function
- Congenital anomaly/birth defect

Important medical events that may not result in death, are life threatening, or require hospitalization may be considered serious when, based upon appropriate medical judgment, they may jeopardize the patient or subject and may require medical or surgical intervention to prevent one of the outcomes listed in this definition. Examples of such medical events include allergic bronchospasm requiring intensive treatment in an emergency room or at home, blood dyscrasias or convulsions that do not result in inpatient hospitalization, or the development of drug dependency or drug abuse.

#### 7.3.2.4 Life-threatening

An adverse event or suspected adverse reaction is considered life threatening if, in the view of either the investigator or sponsor, its occurrence places the patient or subject at immediate risk of death. It does not include an adverse event or suspected adverse reaction that, had it occurred in a more severe form, might have caused death.

#### 7.4 Recording of an Adverse Event

Refer to the Data Safety Monitoring Plan, located in Appendix 4.

#### 7.5 Follow-up of Adverse Events

All participants who experience adverse events will be followed with appropriate medical management until resolved or stabilized, as determined by the investigator, or until the initiation of new anti-cancer therapy, whichever occurs first. Patients removed from study for unacceptable adverse events will be followed until resolution or stabilization of the adverse event. For selected adverse events for which administration of the investigational drug was stopped, a re-challenge of the subject with the investigational drug may be conducted if considered both safe and ethical by the Investigator.

#### 7.6 Adverse Events Monitoring

Refer to the Data Safety Monitoring Plan, located in Appendix 4.

#### 7.7 Expedited Reporting

#### Reporting to the Data and Safety Monitoring Committee

Version date: 07/29/2022

If a death occurs during the treatment phase of the study or within 30 days after the last administration of the IMP(s) and it is determined to be related either to the IMP(s) or to a study procedure, the Investigator or his/her designee must notify the DSMC Chair (or qualified alternate) within 1 business day of knowledge of the event. The contact may be by phone or e-mail.

#### Reporting to UCSF Committee on Human Research (Institutional Review Board)

The UCSF PI must report events to the UCSF IRB according to institutional guidelines.

UCSF IRB website for guidance in reporting adverse events: https://irb.ucsf.edu/adverse-event

#### Expedited Reporting to the FDA

If the study is being conducted under an IND, the Sponsor (or the Sponsor-Investigator) is responsible for determining whether or not the suspected adverse reaction meets the criteria for expedited reporting in accordance with federal regulations (21 CFR §312.32).

The Sponsor (or Sponsor-Investigator) must report in an IND safety report any suspected adverse reaction that is both serious and unexpected. The Sponsor needs to ensure that the event meets all three definitions:

- Suspected adverse reaction
- Unexpected
- Serious

If the adverse event does not meet all three of the definitions, it should not be submitted as an expedited IND safety report.

The timeline for submitting an IND safety report to FDA is no later than **15 calendar days** after the Investigator determines that the suspected adverse reaction qualifies for reporting (21 CFR 312.32(c)(1)).

Any unexpected fatal or life-threatening suspected adverse reaction will be reported to FDA no later than **7 calendar days** after the Investigator's initial receipt of the information (21 CFR 312.32(c)(2)).

Any relevant additional information that pertains to a previously submitted IND safety report will be submitted to FDA as a Follow-up IND Safety Report without delay, as soon as the information is available (21 CFR 312.32(d)(2)).

## 8 Statistical Considerations and Evaluation of Results

#### 8.1 Sample Size Considerations

#### 8.1.1 Sample Size and Power Estimate

For Cohort A: Assuming signal-to-noise ratio of target tumor C pyruvate metabolism of 30 and standard deviation of 5, a sample size of 20 evaluable patients will provide an expected width of 95% confidence intervals of +/-2.2, with a standard error of 1.1.

For Cohort B: A sample size of 20 evaluable patients will allow the detection of a standardized difference of 0.38 with 80% power at a 2-sided significance level of 0.05 using a paired t-test.

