## 8.1.2 Accrual Estimates

It is estimated that 1-2 subject will be enrolled per month, and approximately 36 months will be required to complete accrual and data acquisition to the study. In the case of subjects being unevaluable for analysis of primary endpoint, additional subjects may be enrolled to reach the required total number of evaluable subjects.

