#### 8.3.2 Primary Analysis

Cohort A: Signal-to-noise ratio of C pyruvate metabolism measures (peak C lactate/pyruvate ratio, C lactate/pyruvate AUC ratio, and apparent rate constant for pyruvate-to-lactate conversion, kPL) in the target tumor (primary tumor and/or abdominal metastases).

Cohort B: Percent changes in the target tumor (primary tumor and/or abdominal metastases)  $^{13}$ C pyruvate metabolism measures (peak  $^{13}$ C lactate/pyruvate ratio,  $^{13}$ C lactate/pyruvate AUC ratio, and  $k_{PL}$ ) between pre-treatment scan and scan obtained at 4-week (+/- 2 weeks) following treatment initiation.

Primary endpoint analysis: For Cohort A, the signal-to-noise ratio of the target lesion C pyruvate metabolism measures will be determined for each patient. Descriptive statistics will be used to summarize the mean, standard deviation, and 95% confidence interval of the measurements.

For Cohort B, paired t-test or Wilcoxon signed rank test will be used to compare the target tumor HP C pyruvate metabolism pre- and 4-week (+/- 2 weeks) post treatment initiation.

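### Cohort A's planned 95% CI of ±2.2 is a known-SD approximation; with the SD estimated from 20 patients the expected half-width is about ±2.3, a minor overstatement of precision that leaves n = 20 intact

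*Combined protocol and SAP*

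**What the plan says.** Section 8.1.1 of the combined protocol and SAP gives the planning basis for Cohort A in one sentence. The assumptions are "Assuming signal-to-noise ratio of target tumor 13 C pyruvate metabolism of 30 and standard deviation of 5". The result is that 20 evaluable patients give an "expected width of 95% confidence intervals of +/-2.2, with a standard error of 1.1". The sentence does not name the multiplier and sets no required or maximum interval width.

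Section 8.3.2 gives the matching analysis. The signal-to-noise ratio is determined for each patient, and then: "Descriptive statistics will be used to summarize the mean, standard deviation, and 95% confidence interval of the measurements". No test or decision threshold is attached to Cohort A, and the section does not say whether the interval uses a normal or a t quantile.

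Section 8.1.2 allows for patients who cannot be evaluated: "additional subjects may be enrolled to reach the required total number of evaluable subjects". The calculation can therefore take n = 20 as given.

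**The concern.** A planning figure for an interval should match the interval that will be reported. Here the standard deviation is an assumption at the planning stage but an estimate at the analysis stage, taken from 20 observations. With 19 degrees of freedom the 95% multiplier is 2.093, not 1.96, and the difference is large enough to move the first decimal of the stated half-width.

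This sentence is the only quantitative support for the size of Cohort A. A reader who rebuilds the interval at the assumed standard deviation will get about ±2.3 where the plan says ±2.2. What is at stake is the accuracy of that one figure; no decision in the trial depends on it.

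**Working it through.** **Inputs.** All are from section 8.1.1: standard deviation 5, 20 evaluable patients, 95% confidence. The ± notation implies a two-sided interval. The assumed mean of 30 does not enter the half-width. The t results below assume roughly normal measurements.

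**Step 1: reproduce the plan's figures.**
- Standard error = SD/√n = 5/√20 = 1.118, stated as 1.1. It agrees.
- Half-width with the normal quantile = 1.960 × 1.118 = 2.191, stated as 2.2. It agrees.
- Half-width with the multiplier 2 = 2 × 1.118 = 2.236, which also rounds to 2.2.

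The rounded figures cannot tell these two multipliers apart. Both treat the standard deviation as known.

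**Step 2: use the t quantile.** Section 8.3.2 summarises the standard deviation from the data, so the multiplier is t(0.975, 19) = 2.093.
- Half-width when the sample standard deviation equals 5: 2.093 × 1.118 = 2.340.
- Expected half-width: the sample standard deviation averages slightly below the true value, by the factor c₄ = √(2/(n−1)) × Γ(n/2)/Γ((n−1)/2). For n = 20, c₄ = 0.9869, so the expected half-width is 0.9869 × 2.340 = 2.309.

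Both round to 2.3. Section 8.1.1 speaks of an expected interval, so 2.31 is the closer counterpart of the plan's figure.

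**Step 3: size of the gap.**
- Against the stated figure, in expectation: 2.31/2.2 = 1.05, or 5%.
- Against the unrounded normal figure: 2.309 − 2.191 = 0.12 in expectation, and 2.340 − 2.191 = 0.15 at SD 5, which is 5% to 7%.
- Relative to the assumed mean: 0.12/30 = 0.4% and 0.15/30 = 0.5%.

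**Step 4: the gap in patients.** With SD 5:

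| n | t half-width at SD 5 | Expected t half-width |
|---|---|---|
| 20 | 2.340 | 2.31 |
| 21 | 2.276 | 2.25 |
| 22 | 2.217 | 2.19 |
| 23 | 2.162 | not needed |

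On the expected half-width, about 22 patients give 2.2.

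**Step 5: comparison with the uncertainty in the assumed SD.** At n = 20 the t half-width is 2.093/√20 = 0.468 times the standard deviation.
- SD 4: 1.87
- SD 4.7: 2.20
- SD 5: 2.34
- SD 6: 2.81

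Moving from the normal to the t quantile has the same effect as changing the standard deviation by about 0.3.

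**The case against.** The strongest reply is that there is no miscalculation. The plan's figures follow from its own inputs, the sentence is openly conditional on the assumed standard deviation, and treating that value as known is a common planning shortcut. That stands: ±2.2 is an approximation, not an arithmetic slip. It does not settle the matter, because the plan does not say that it is approximating and the t-based answer differs at the one decimal reported.

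A second reply is that nothing depends on the difference. The plan sets no precision target, Cohort A is descriptive, the study is a pilot, and a modest error in the assumed standard deviation would matter more. This also stands, and it limits the point to a correction of wording.

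Three stronger readings are tempting, and the documents do not support them.
- A reader might infer that the reported interval will cover less than 95%. An interval of ±1.96 standard errors with 19 degrees of freedom covers about 93.5% under normality. But section 8.3.2 does not say that the final interval will use 1.96, and for Cohort B the plan names a paired t-test. The under-coverage would follow from a choice that the plan has not made.
- A reader might infer that 23 patients are needed. That number comes from requiring the half-width at SD 5, unrounded, to be no more than 2.2. The plan speaks of an expected interval, and on that basis 22 patients already give 2.19.
- A reader might object that a half-width is called a width. The ± sign and the standard error of 1.1 leave no doubt about what is meant.

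**Conclusion.** The point holds as a minor one. Section 8.1.1 states a precision of ±2.2 that matches a known-SD approximation. The t-based expected half-width for 20 patients is 2.31, or 2.34 when the sample standard deviation equals 5, so the stated precision is about 5% too favourable.

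The result rests on the plan's own standard deviation and sample size, on roughly normal measurements, and on the final interval being the ordinary t interval for a mean. It does not undermine n = 20: a reader might take it to show that the cohort is too small, but the plan sets no width that ±2.3 would fail to meet.

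**What to change.** Reword the Cohort A sentence in section 8.1.1, for example: *with SD 5 and 20 evaluable patients, the 95% confidence interval (t distribution, 19 df) has an expected half-width of about 2.3 (SE 1.1)*. Leave the sample size as it is.

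Optionally, add to section 8.3.2 that the Cohort A interval is t-based. This would settle the method before analysis and keep it in line with the planning figure.

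The cost is one sentence, plus a few words if the optional note is added, and a stated precision that looks slightly less favourable. Enrolment and data collection do not change; the optional note only makes the interval method explicit.

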#### 8.3 Analysis Plans

Data from all subjects dosed in the study will be included in all listings, plots, summary tables, and statistical analyses when appropriate. Missing values will not be substituted by estimated values, but treated as missing in the statistical evaluation.

In this pilot study, we will focus on the primary PDA HP C pyruvate metabolism (if present) because accurate assessment of treatment response in the primary PDA is particularly challenging on conventional imaging given its infiltrative nature(10). If the primary tumor has been resected, we will then focus our analysis on the largest abdominal metastasis that is amenable to HP MRI.

We will not explicitly adjust for multiple comparisons in analyzing the data in this pilot study.

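### Cohort B power statement: 20 pairs detect a standardized difference of 0.66 with 80% power, not 0.38; power at 0.38 is about 36%

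*Combined protocol and SAP*

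**What the plan says.** Section 8.1.1 justifies the Cohort B sample size in one sentence: "A sample size of 20 evaluable patients will allow the detection of a standardized difference of 0.38 with 80% power", and continues "at a 2-sided significance level of 0.05 using a paired t-test". It does not say which SD standardizes the difference, and it gives neither an SD nor a pre/post correlation.

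Section 8.3.2 defines the Cohort B primary endpoint as the within-patient percent change in the tumor pyruvate measures from baseline to the scan at 4 weeks (+/- 2 weeks). The planned test is given as "paired t-test or Wilcoxon signed rank test will be used to compare the target tumor HP" measures before and after the start of treatment.

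Two other places fix the inputs. Section 8.3 says "We will not explicitly adjust for multiple comparisons in analyzing the data in this pilot study", so the level stays at 0.05 per test. Section 8.1.2 allows further enrolment to make up for unevaluable patients, so 20 is the number analysed and not a number to be reduced for dropout.

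**The concern.** A paired t-test on 20 pairs is a one-sample t-test on 20 differences. As a rough check, 80% power at two-sided 0.05 needs a standardized difference of about 2.8/√20, or roughly 0.63. A value of 0.38 is far below that, and rounding or the choice of approximation cannot explain the gap.

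The sentence is the only statement of what the Cohort B primary comparison can detect. If it is wrong, a reader of a non-significant result would believe the study had an 80% chance of finding a change of 0.38 SD when it had much less. Anyone who used the sentence to plan a later study of the same effect would also start from too small a sample.

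**Working it through.** **Inputs, all from Section 8.1.1:** n = 20 evaluable pairs; paired t-test; two-sided α = 0.05; power 80%; stated detectable difference 0.38.

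**Definition used:** d = mean of the paired differences / SD of the paired differences, the usual scale for a paired t-test.

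**Formula.** Under a true difference d the test statistic follows a noncentral t distribution with n − 1 degrees of freedom and noncentrality δ = d√n. Power is P(|T| > t₀.₉₇₅,ₙ₋₁).

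**Step 1: try to reproduce the stated figure.**
- df = 19, critical value 2.093.
- δ = 0.38 × √20 = 1.699.
- Power = P(T > 2.093) + P(T < −2.093) = 0.3646 + 0.0002 = **36.5%**, not 80%. A simulation of 200,000 trials gives 36.7%.

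**Step 2: the difference that 20 pairs do detect with 80% power.**
- Solving for d gives **0.660** (δ = 0.660 × √20 = 2.95).
- Normal approximation: (1.960 + 0.842)/√20 = 0.626.
- Ratio to the stated value: 0.660/0.38 = 1.74.

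**Step 3: pairs needed to detect 0.38.**
- n = 56 gives 79.8% and n = 57 gives 80.5%, so **57 pairs**.
- Normal approximation: ((1.960 + 0.842)/0.38)² = 54.4, so 55.

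**Step 4: other readings of the inputs.**

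| Reading | Detectable d at 80% power | Power at 0.38 |
|---|---|---|
| As stated (20 pairs, two-sided 0.05) | 0.660 | 36.5% |
| One-sided 0.05 | 0.577 | 49.7% |
| Two-sided 0.20 | 0.485 | 65.0% |
| 40 pairs, two-sided 0.05 | 0.454 | 64.9% |
| One-sided 0.20 | 0.380 | 80.0% |

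Only one-sided 0.20 matches, and it contradicts the stated two-sided 0.05. It may point to an input slip, but that is an inference.

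**Step 5: standardizing by the single-scan SD.** If the SD is the same at both scans and the pre/post correlation is ρ, then SD of differences = SD × √(2(1 − ρ)). The detectable difference in single-scan SDs is therefore 0.660 × √(2(1 − ρ)). The documents give no ρ, so the range below is an assumption.

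| ρ | Detectable difference (single-scan SDs) | Power at 0.38 |
|---|---|---|
| 0.3 | 0.78 | 27.6% |
| 0.5 | 0.66 | 36.5% |
| 0.7 | 0.51 | 54.9% |
| 0.8 | 0.42 | 72.2% |
| 0.9 | 0.30 | 95.0% |

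Setting the result to 0.38 gives ρ = 1 − (0.38/0.660)²/2 = 0.83.

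**Step 6: if the Wilcoxon test is used instead.** Assuming normally distributed differences and an asymptotic efficiency of 0.955, the detectable difference is about 0.660/√0.955 = 0.68. This does not help.

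**The case against.** The best defence is that Section 8.1.1 never names its standardizing SD. Section 8.3.2 describes the test as a comparison of values before and after treatment starts, so a reader could take the SD to be that of a single scan. On that scale 0.38 is correct if the pre/post correlation is about 0.83, and the documents do not rule that out. This stands as a possible explanation, but it does not rescue the sentence. The correlation is not stated, the result depends heavily on it (Step 5), and the endpoint is a within-patient percent change, whose natural scale is the SD of the changes. On this reading the plan leaves out the assumption that carries the whole figure.

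A second argument is that this is a pilot, with no futility rule or go/no-go decision tied to 0.38, so the practical harm is limited. That is fair as to consequences: conduct, test and endpoint are unaffected, and how a null result or a later plan would use the figure is a matter of judgement. Pilot status excuses a small sample. It does not excuse a wrong statement of what that sample can detect.

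**Conclusion.** The concern holds. Under the stated test, level, sidedness and sample size, and with the difference in SDs of the paired changes, the detectable difference is 0.66 and not 0.38. Type II error at 0.38 is 63.5% instead of 20%. The result assumes normally distributed differences and 20 analysed pairs. Nothing in Sections 8.1.2, 8.3 or 8.3.2 repairs the figure. The one open question is whether the authors meant single-scan SDs; if so, the sentence is incomplete and still needs correction.

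**What to change.** Replace the Cohort B sentence in Section 8.1.1 with wording to this effect: *With 20 evaluable patients, a paired t-test at the two-sided 0.05 level has 80% power for a mean paired change of 0.66 SDs, where the SD is that of the paired changes; power for a change of 0.38 SDs is about 36%.*

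If 0.38 was meant in single-scan SDs, say so, state the assumed pre/post correlation (about 0.83) with its justification, and show the detectable difference over a plausible range of correlations.

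The cost is one sentence and a less favourable stated effect. Enrolment, endpoint and test stay as they are. Keeping 0.38 at 80% power on the paired-change scale would instead take 57 evaluable pairs, which this correction does not ask for.
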